**Study on the Diagnostic Accuracy of Endoscopic Ultrasound for Colorectal
Subepithelial Lesions**

NCT number: not yet assigned

Document date: 2023.11.20

1. Background

On endoscopic ultrasound (EUS), the normal intestinal wall is typically visualized as a five-layer structure with alternating hyperechoic and hypoechoic layers, corresponding to the superficial mucosal interface, deep mucosa/muscularis mucosa, submucosa, muscularis propria, and serosa. For subepithelial lesions (SELs), EUS can measure lesion size and assess sonographic features such as margins, homogeneity, and acoustic shadowing. It also provides information on the layer of origin, lesion location, and relationship to surrounding tissues. By integrating these findings, EUS may help predict pathological nature and guide subsequent management.

However, compared with final histopathology, the reported diagnostic accuracy of EUS for gastrointestinal SELs is approximately 43%–79%, which may not fully meet current clinical needs.

2. Objectives

2.1 Primary Objective

To identify factors associated with the coincidence (concordance) between EUS diagnosis and pathological diagnosis for colorectal subepithelial lesions.

3. Endpoints

3.1 Primary Endpoint

Coincidence rate between EUS diagnosis and pathological diagnosis.

4. Study Design

This is a single-center, retrospective, observational study. All patients who underwent colorectal EUS at Shenzhen Hospital of Southern Medical University between 2015 and 2023 will be screened, and their endoscopy/EUS reports and pathology reports will be retrospectively reviewed and analyzed.

If a patient had two or more colorectal lesions evaluated by EUS, lesions at different sites will be treated as independent EUS examinations. Only SEL cases with histopathologic confirmation will be included for further analysis.

During the study, no randomization will be performed and no protocol-driven treatment will be administered or provided. When clinically indicated, treatment decisions and treatment selection will be made at the discretion of the treating physician.

5. Study Population

The study population consists of patients with colorectal subepithelial lesions.

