6.4 Data Collection Items

1. Demographics: age, sex, initials;
2. Lesion location and size (maximum diameter);
3. EUS echogenic features, layer-related characteristics, EUS diagnosis (primary diagnosis), operator, and device information;
4. Pathology acquisition method, pathological layer, and pathological diagnosis.

7. Criteria for Study Termination / Suspension

7.1 The sponsor has the right to terminate or suspend the study. Before termination/suspension, the sponsor must notify the investigator, the ethics committee, and relevant regulatory authorities and provide the rationale. If the study is terminated/suspended early, restarting the study requires ethics committee approval.

7.2 Termination or suspension as required by the ethics committee.

8. Study Completion

The study will be completed when data collection reaches the predefined time interval.

9. Data Management

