10.1 Sample Size Determination

This is a single-center, retrospective, observational study. One-way analysis of variance (ANOVA) will be used to explore factors associated with concordance versus non-concordance between EUS diagnosis and pathological diagnosis. Using G*Power (version 3.1.9.7) with an effect size of 0.25, $\alpha = 0.05$, power $(1-\beta) = 0.80$, 10 predictors, and 2 groups, the required sample size was calculated to be 269 cases.

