10.3 Statistical Software and General Requirements

- Statistical analyses will be performed using SPSS.
- Continuous variables will be summarized using mean, standard deviation, median, minimum, and maximum values.
- Categorical variables will be summarized using frequencies and percentages.
- One-way ANOVA will be used to evaluate differences in potential factors between the concordant and non-concordant groups.
- Multivariable logistic regression will be performed to identify key factors independently associated with diagnostic concordance.

11. Study Management

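### Several lesions from one patient are treated as independent, so tests of patient-level factors can be too liberal

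*Combined protocol and SAP*

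**What the plan says.** Section 4 (Study Design) foresees patients with two or more colorectal lesions examined by EUS and states that "lesions at different sites will be treated as independent EUS examinations". The only later filter is histology: "Only SEL cases with histopathologic confirmation will be included for further analysis". Nothing limits a patient to one lesion.

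Section 10.3 plans two analyses of factors: "One-way ANOVA will be used to evaluate differences in potential factors between the concordant and non-concordant groups", and "Multivariable logistic regression will be performed to identify key factors independently associated with diagnostic concordance". Neither sentence names a random effect, GEE or cluster-robust standard errors, and no other section does. For the coincidence rate itself, section 10.3 offers only description: "Categorical variables will be summarized using frequencies and percentages".

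Section 10.1 states that "the required sample size was calculated to be 269 cases", without saying whether a case is a patient or a lesion and without a design effect.

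The candidate factors in section 6.4 are of two kinds. Some belong to the patient ("Demographics: age, sex, initials"). Others belong to the lesion (location, maximum diameter, echogenic features, layer). Operator and device fall between: they are shared when a patient's lesions were examined by the same operator with the same device.

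**The concern.** Two lesions in one patient may have been examined by the same operator, in the same session and with the same device. It is plausible that EUS and pathology agree for both or for neither more often than chance would give. Both planned analyses treat each row as a separate piece of information. For a factor that is the same for all of a patient's lesions, the second lesion then counts as a full new observation when it is not, and the standard error is too small. For a contrast between lesions of the same patient the error runs the other way, and the p-value is too large.

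The primary objective (section 2.1) is to name factors associated with concordance, so the validity of these tests is what the study delivers. A patient-level factor could be declared associated more often than 5% of the time under the null. The test of a factor that contrasts lesions within patients would be conservative. Any confidence interval for the coincidence rate computed under the independence rule would be too narrow if the within-patient correlation is positive. The plan does not require the number of patients behind the lesions to be reported, so a reader might be unable to judge the matter.

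**Working it through.** **Step 1: the plan's own figure.** Inputs from section 10.1: effect size f = 0.25, α = 0.05, power 0.80, 10 predictors, 2 groups. With the noncentral F distribution, numerator df = 10, denominator df = N − 2 and noncentrality λ = f²N, the smallest N reaching 80% power is 269 (λ = 0.0625 × 269 = 16.81, denominator df 267, power 0.8003). The figure of 269 is thus reproduced, with every case counted as independent. (A two-group one-way ANOVA has numerator df 1 and would need 128. That is a separate matter and does not affect this point.)

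**Step 2: design effect.** The documents give neither the share q of patients with two included lesions nor the intraclass correlation (ICC) of concordance, so both are assumed. All other patients have one lesion. For a factor constant within the patient, and for the overall rate:

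- Σm²/Σm = (1 + 3q)/(1 + q), where m is the number of lesions per patient
- DE = 1 + (Σm²/Σm − 1) × ICC = 1 + [2q/(1 + q)] × ICC
- true SE / naive SE = √DE; effective N = 269/DE; patients = 269/(1 + q)
- true size of a nominal 5% test = 2 × [1 − Φ(1.96/√DE)]

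| q | ICC | Patients | DE | SE increase | Effective N | True size |
|---|---|---|---|---|---|---|
| 5% | 0.1 | 256 | 1 + 0.0952 × 0.1 = 1.0095 | 0.5% | 266 | 5.1% |
| 20% | 0.5 | 224 | 1 + 0.3333 × 0.5 = 1.167 | 8.0% | 231 | 7.0% |
| 30% | 0.6 | 207 | 1 + 0.4615 × 0.6 = 1.277 | 13.0% | 211 | 8.3% |

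For a binary factor forced to differ between the two lesions of every two-lesion patient, the sign reverses. At the upper corner DE = 1 − 0.4615 × 0.6 = 0.723, and the true size is 2.1%.

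**Step 3: simulation with logistic regression.** 269 lesions, 10,000 runs per cell, one balanced binary factor with no effect. The second lesion copies the first lesion's concordance with probability equal to the ICC. True concordance was set to 43% and 79%, the ends of the accuracy range that section 1 gives for gastrointestinal lesions. Rejection rates at nominal 5% are shown as 43% / 79%:

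| Setting | Factor | Ordinary SE | Cluster-robust SE |
|---|---|---|---|
| 62 of 207 patients with two lesions, ICC 0.6 | patient-level | 8.1% / 8.0% | 4.9% / 5.0% |
| same | varies independently by lesion | 5.3% / 4.6% | 5.3% / 4.6% |
| same | forced within-patient contrast | 1.9% / 2.1% | 5.0% / 5.1% |
| 13 of 256 patients with two lesions, ICC 0.1 | patient-level | 5.2% / 5.0% | not tabulated |
| same | varies independently by lesion | 5.1% / 4.5% | not tabulated |
| same | forced within-patient contrast | 4.7% / 4.6% | not tabulated |

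**Step 4: simulation with the planned one-way ANOVA.** 269 lesions, 20,000 runs per setting, assumed concordance 60%, ICC 0.2 to 0.8. For a continuous factor shared within the patient, the type I error was 5.3%–5.8% (q = 5%), 5.3%–6.4% (q = 10%) and 5.9%–7.9% (q = 20%). For a factor varying independently between lesions it was 4.8%–5.2% across the same settings. With no multi-lesion patients it was about 5% for both kinds.

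**The case against.** The strongest reply is that the consequence rests wholly on assumed inputs and is probably small. A patient enters twice only if both lesions are subepithelial and both have histology, which may be uncommon. With 10% of patients and ICC 0.3 the true size is 5.6%; with 5% and ICC 0.6 it is 5.7%. Only the assumed extreme reaches 8.3%. Few factors are exposed: age and sex, and possibly operator and device. Most factors of interest belong to the lesion and keep close to nominal error if they vary independently. The 2% figure describes a factor made to differ in every two-lesion patient, which no factor in section 6.4 is shown to do, and no power loss was calculated. The logistic simulation has a single factor, whereas the deciding model is multivariable; adjustment for operator, device or layer could absorb part of the correlation. Finally, section 4 can be read as only fixing the unit of counting, section 6.2 already supplies a participant number, and section 10.2 plans descriptions of cases and demographics.

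Much of this stands as a limit on size. The 8% is not shown for the multivariable model, the missed-factor risk is a possibility rather than an estimate, and patient counts might be reported even though the plan does not require it. None of it removes the defect. The plan states independence as a rule and supplies no variance method, and the participant number appears in neither analysis in section 10.3. Read merely as a counting rule, section 4 still leaves both analyses treating rows as independent.

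**Conclusion.** The concern holds. Followed as written, the plan gives wrong standard errors for patient-shared factors whenever three conditions are met: some patients contribute more than one confirmed lesion, concordance is positively correlated within patients, and the factor is common to a patient's lesions. All three can occur, and nothing in the plan guards against them.

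The size is modest. Over the assumed range (5%–30% of patients with two lesions, ICC 0.1–0.6) standard errors for a patient-level factor or the rate are 0.5%–13% too small relative to the naive value, and the true type I error is 5.1%–8.3%. Lesion-level factors that vary independently are essentially unaffected. The multi-lesion share and the ICC are assumptions throughout. The plan should be changed: the better method is inexpensive and gives nearly the same answer if clustering turns out to be negligible.

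**What to change.** Replace the independence sentence in section 4 and extend section 10.3 along these lines:

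> The lesion is the unit of analysis. Every lesion row carries the participant identification number, which is the same for all lesions of a patient. The numbers of patients, of lesions, and of patients with two or more included lesions are reported. Univariable comparisons (in place of one-way ANOVA) and the multivariable model take concordance as the outcome and are fitted by logistic GEE, or by logistic regression with standard errors clustered on participant. The coincidence rate is reported with a cluster-robust 95% confidence interval. A sensitivity analysis uses one lesion per patient, either the first examined or one drawn at random with a recorded seed.

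The sensitivity lesion should not be chosen by size, because maximum diameter is itself a candidate factor. Section 10.1 should say whether its 269 cases are patients or lesions.

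The cost is a change of wording and a GEE or cluster-robust procedure, available in SPSS, which is the planned software. Intervals for patient-level factors and for the rate widen by at most about 13% in the assumed range. The analysis takes slightly more work, and no new data are needed.

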5.2 Inclusion Criteria

1. Patients admitted to Shenzhen Hospital of Southern Medical University from 2015 to 2023 who underwent colorectal EUS.
2. Patients diagnosed with colorectal submucosal tumors (subepithelial lesions) according to the Chinese expert consensus on endoscopic diagnosis and treatment of gastrointestinal submucosal tumors (2023 edition) and related criteria.

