5.3 Exclusion Criteria

1. Patients whose EUS diagnosis indicated non-submucosal tumors (i.e., not consistent with submucosal tumors/subepithelial lesions).

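### Section 4's histology rule has two readings; under one of them, EUS-called SELs that pathology refutes drop out and the coincidence rate rises

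*Combined protocol and SAP*

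**What the plan says.** The sole endpoint (Section 3.1) is the "Coincidence rate between EUS diagnosis and pathological diagnosis". Section 2.1 asks which factors go with concordance, and Section 10.3 answers by comparing concordant with non-concordant groups and fitting a logistic model.

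Four statements decide which lesions enter:

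- Section 4, on histology: "Only SEL cases with histopathologic confirmation will be included for further analysis".
- Section 5.2(2), on inclusion: "Patients diagnosed with colorectal submucosal tumors (subepithelial lesions) according to the Chinese expert consensus". It does not say whether that diagnosis comes from EUS or from pathology.
- Section 5.3, on exclusion: "Patients whose EUS diagnosis indicated non-submucosal tumors (i.e., not consistent with submucosal tumors/subepithelial lesions".
- Section 4, on the unit when a patient has several lesions: "lesions at different sites will be treated as independent EUS examinations".

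Neither Section 10.2 nor Section 10.3 says what happens to a lesion that EUS called SEL and pathology shows is not one.

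**The concern.** In ordinary usage, a case with histological confirmation is often one in which histology established the condition. If Section 4 is applied that way, the reference standard helps decide who is analysed. Section 5.3 has already removed lesions that EUS did not call SEL, so both tests would have to agree that the lesion is an SEL before it counted. The lesions lost at this step are all EUS errors of one kind, and they are among the cases that the factor analysis is meant to explain.

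The sentence sets the denominator of the only endpoint, so two careful analysts could report different rates from the same records. The order of work adds to this. EUS and pathology reports are reviewed together (Section 4), investigators determine eligibility from the records (Section 6), and no masking of that step to the pathology result is described. An open rule could thus be settled with the outcome in view.

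There is also a smaller mismatch: 5.2 and 5.3 are worded for patients, while Section 4 counts lesions. Read literally, a patient with one eligible SEL and one non-SEL lesion elsewhere would lose both.

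**Working it through.** **Setting the passages side by side.** Section 5.3 limits the set to lesions that EUS called SEL. Section 4 then adds a condition on histology:

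- Reading (a), histology is available: a lesion called SEL by EUS with non-SEL pathology stays in and counts as non-concordant.
- Reading (b), histology confirmed SEL: the same lesion is removed.

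Section 5's description of the population as patients with colorectal SELs fits (b). The reference in 5.3 to the EUS diagnosis, and the endoscopic consensus cited in 5.1 and 5.2, fit (a). No passage settles it.

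**Inputs.** The plan states no expected coincidence rate for this study and no share of EUS-called SELs with non-SEL pathology. Let n be the number of EUS-called SELs with histology, c the proportion concordant, and x the proportion whose pathology is not SEL. Both c and x are assumed. For c, 70% is used as the main illustration. The ends of the 43% to 79% range that Section 1 reports for gastrointestinal SELs serve as outer values.

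**Formula.** Under (a) the rate is cn/n = c. Under (b), xn lesions go, all of them discordant, so the numerator stays at cn and the denominator becomes n(1 − x). The rate is c/(1 − x).

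| c | x = 5% | x = 10% | x = 15% |
|---|---|---|---|
| 43% | 45.3% (+2.3) | 47.8% (+4.8) | 50.6% (+7.6) |
| 70% | 73.7% (+3.7) | 77.8% (+7.8) | 82.4% (+12.4) |
| 79% | 83.2% (+4.2) | 87.8% (+8.8) | 92.9% (+13.9) |

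Brackets show the rise in percentage points. For example, 0.70/0.90 = 0.778.

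**Loss from the non-concordant group.** The share lost is x/(1 − c). For c = 70% and x = 10% it is 0.10/0.30 = 33%. To put this in counts, take the plan's 269 cases (Section 10.1) as n. That figure reproduces as an F test with effect size 0.25, 10 numerator degrees of freedom and 2 groups (power 0.8003), and it does not depend on this point. With x = 10%, 0.10 × 269 ≈ 27 lesions go:

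- c = 43%: 269 − 116 = 153 non-concordant lesions, falling to 126.
- c = 79%: 269 − 213 = 56 non-concordant lesions, falling to 29.

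**Limiting case.** The plan does not say at what level agreement is judged. If it were judged only as SEL versus not SEL, then c = 1 − x, and reading (b) would give (1 − x)/(1 − x) = 100% by construction.

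**The case against.** The strongest reply is that (a) is what was meant. Section 5.3 defines SEL status by EUS, and 5.1 and 5.2 rest on a consensus about endoscopic diagnosis, so 5.2(2) reads comfortably as a diagnosis made before pathology. Section 4 never says that a lesion is removed because pathology disagrees. This stands: (a) is as tenable as (b). A reader might infer that the plan does drop false-positive EUS calls and does inflate its endpoint. The document does not support that. It supports only that one literal application would do so.

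A second reply is that (b) may be a deliberate choice of population. Section 2.1 speaks of concordance for colorectal SELs, and the items in Section 6.4 suggest agreement on lesion type. Type agreement among proven SELs is a legitimate, narrower target, and disagreements about type would remain for the factor analysis. This stands in part. The rise to c/(1 − x) is an inflation only if the target is all EUS-called SELs. But the plan does not state the narrower target. Section 1 motivates the work by EUS predicting pathology and guiding management, which happens before pathology is known.

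Third, the sizes are not grounded. No x is given, and the denominators behind the 43% to 79% range cannot be seen. Some cells are also strained: at c = 79% and x = 15%, non-SEL histology would make up 0.15/0.21 = 71% of all discordance. This stands, so the table shows direction and scale and is not an estimate.

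Finally, an exclusion worded on the EUS diagnosis can naturally be applied per examination. The patient-versus-lesion wording may therefore be loose drafting, and no link between such losses and concordance has been shown.

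**Conclusion.** The point holds as a conditional one. Section 4's inclusion sentence admits two readings and the document does not choose. Under (b), the rate among EUS-called SELs rises by the factor 1/(1 − x) for any x above zero, and the lesions lost come entirely from the non-concordant group. Under (a) the effect is nil. The direction under (b) follows from algebra; the size rests wholly on assumed values of c and x.

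It would be wrong to conclude that the endpoint is biased as planned, or that the patient-level wording of 5.2 and 5.3 biases it. The latter is a drafting inconsistency with a probably small effect. The whole point is best treated as a cheap improvement.

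**What to change.** Replace the Section 4 sentence with: *All lesions called SEL by EUS that have a definitive histopathological diagnosis of any kind are included; a pathological diagnosis that is not an SEL counts as non-concordant.*

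As a minor drafting change, word 5.2(2) and 5.3 for the lesion, so that a non-SEL lesion elsewhere does not remove an eligible one.

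This rewording settles how non-SEL pathology is counted. It does not define agreement among lesions that are SELs on both tests, which the endpoint definition still has to state.

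The cost is two or three sentences, taken through the amendment and ethics steps of Section 11.3. The EUS and pathological diagnoses needed are already listed in Section 6.4, so no new data are required. The downside is that the reported rate may be less favourable than under reading (b). If (a) was always intended, the change simply records it.

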5.1 Diagnostic Criteria

Diagnosis of colorectal submucosal tumors/subepithelial lesions will be based on the Chinese expert consensus on endoscopic diagnosis and treatment of gastrointestinal submucosal tumors (2023 edition).

5.2 Inclusion Criteria

1. Patients admitted to Shenzhen Hospital of Southern Medical University from 2015 to 2023 who underwent colorectal EUS.
2. Patients diagnosed with colorectal submucosal tumors (subepithelial lesions) according to the Chinese expert consensus on endoscopic diagnosis and treatment of gastrointestinal submucosal tumors (2023 edition) and related criteria.

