6.2 Participant Identification Number

Each participant will be assigned a unique identification number in chronological order based on the date of examination. All study documents (e.g., case report forms, clinical records) will use this identification number. In accordance with data privacy regulations, the identification number must not include combinations that could identify the participant (e.g., initials plus date of birth should not be used together).

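### The plan does not require the EUS diagnosis to be made before the pathology was known, so the coincidence rate and the factor analysis could be biased, most likely upward

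*Combined protocol and SAP*

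**What the plan says.** The rules that decide which EUS examinations enter the analysis are spread over four sections.

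- **Entry (5.2).** The first criterion is "Patients admitted to Shenzhen Hospital of Southern Medical University from 2015 to 2023 who underwent colorectal EUS". The second requires a diagnosis of a colorectal subepithelial lesion (SEL) under the 2023 Chinese consensus.
- **Histology (4, Study Design).** "Only SEL cases with histopathologic confirmation will be included for further analysis". The same section treats lesions at different sites as separate examinations. It does not address repeat EUS of one lesion.
- **Exclusion (5.3).** The only criterion is "Patients whose EUS diagnosis indicated non-submucosal tumors (i.e., not consistent with submucosal tumors/subepithelial lesions".
- **Data items (6.4).** The EUS items are "EUS echogenic features, layer-related characteristics, EUS diagnosis (primary diagnosis), operator, and device information". The pathology items are "Pathology acquisition method, pathological layer, and pathological diagnosis".

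The sole endpoint (3.1) is "Coincidence rate between EUS diagnosis and pathological diagnosis", with no condition on timing or on what the endosonographer knew. An examination date appears only in 6.2, for numbering participants: "Each participant will be assigned a unique identification number in chronological order based on the date of examination". Background (section 1) gives the intended role of the test: "EUS may help predict pathological nature and guide subsequent management".

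**The concern.** A coincidence rate measures EUS performance only if the EUS diagnosis was reached without the pathology result. In the usual sequence, EUS and then biopsy or resection, this holds. But a lesion may already have a diagnostic biopsy, or may have been removed, before EUS is done to assess depth or look for residual tumour. Such a lesion meets every entry rule. Its EUS report can carry the known diagnosis forward and is then scored as a coincidence. The same can happen when a lesion had several EUS examinations and one performed after histology is the one paired with it.

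Two results are exposed. The first is the coincidence rate, the only endpoint. The second is the factor analysis, the only objective: a factor linked to having had prior histology could look like a determinant of EUS accuracy. The logistic model in 10.3 cannot adjust for prior histology, because 6.4 does not collect it.

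**Working it through.** **1. Is the order fixed anywhere?** Sections 5.2 and 4 require an EUS and a histology but give no sequence or interval. Section 5.3 acts on what the EUS called the lesion, not on what was known beforehand. Section 6 has investigators check eligibility from the medical history, but there is no timing criterion for them to apply. Section 1 describes a predictive use of EUS, which shows intent but does not restrict entry.

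**2. Can the listed data show the order?** The numbering rule in 6.2 implies that an examination date is known. Section 6.4 lists no date for either test and no prior-sampling status. The acquisition method says how tissue was obtained, not when. The order is therefore not available from the listed fields, although it can be retrieved from the reports under review.

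**3. Size of the bias in the rate.** Let *p* be the true concordance, *s* the share of analysed examinations reported with pathology already known, and *k* the concordance among those.

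Observed rate = (1 − s)p + sk, so bias = s(k − p).

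Inputs: *p* = 43% and 79%, the ends of the range cited in section 1. The values of *s* (2% to 20%) and *k* (90% to 100%) are assumptions; the documents give neither.

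Bias in percentage points:

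| s | p = 43%, k = 90% | p = 43%, k = 100% | p = 79%, k = 90% | p = 79%, k = 100% |
|---|---|---|---|---|
| 2% | +0.94 | +1.14 | +0.22 | +0.42 |
| 5% | +2.35 | +2.85 | +0.55 | +1.05 |
| 10% | +4.70 | +5.70 | +1.10 | +2.10 |
| 20% | +9.40 | +11.40 | +2.20 | +4.20 |

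Example: s = 10%, k = 100%, p = 43% gives 0.10 × (1.00 − 0.43) = 0.057.

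**4. Comparison with sampling error.** The planned 269 cases (10.1) reproduce from a noncentral F with f = 0.25, numerator df 10, denominator df N − 2 and λ = N × 0.0625, which gives power 0.8003 at N = 269. This figure does not depend on timing and serves here only as a sample size. The 95% half-width, 1.96 × √(p(1 − p)/269), is 5.9 points at 43% and 4.9 points at 79%. At shares of 2% to 5% the bias is at most 2.85 points, inside that half-width. At 10% and p = 43% it is about equal to it. Unlike sampling error, it does not shrink as cases are added.

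**5. Direction.** The bias is positive only if k > p. That is expected where the reader knew the diagnosis of a lesion still in place. For a scar still labelled an SEL, k could fall below p. At the extreme k = 0 with s = 5%, 43% would be observed as 40.85% and 79% as 75.05%.

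**6. Factor analysis.** Take two lesion sites with equal true accuracy and k = 0.95 (assumed). With shares of 30% and 5%:

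- p = 43%: observed 0.586 and 0.456, odds ratio (0.586/0.414)/(0.456/0.544) = 1.69.
- p = 79%: observed 0.838 and 0.798, odds ratio 1.31.

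With shares of 10% and 2%:

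- p = 43%: observed 0.482 and 0.4404, odds ratio 1.18.
- p = 79%: observed 0.806 and 0.7932, odds ratio 1.08.

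The first contrast is large. Nothing in the documents shows that either occurs.

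**The case against.** The strongest reply is that nothing shows that a post-histology EUS exists in this series. A reader might infer from the missing rule that the coincidence rate *is* inflated. The documents do not support that: they support a risk of unknown size. If such patients are rare, the bias is small against the sampling error. This stands, and it limits the claim to what could happen.

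A reader might also infer that every EUS after removal pushes the rate up. It need not. Inclusion requires an SEL, and 5.3 drops an EUS that does not report one, so many examinations of an empty site or scar fall out. Those still labelled an SEL may be discordant. This also stands. It does not help with a lesion biopsied and left in place, and 5.3 keeps post-removal examinations labelled with the known diagnosis.

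A third tempting reading is that the order of the two tests is lost. It is not: section 4 has the EUS and pathology reports reviewed, and 6.3 draws the data from the medical records. What is missing is the instruction to extract the order and a rule for using it.

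Finally, excluding every lesion sampled before EUS would go too far. A prior non-diagnostic biopsy gives the endosonographer no pathological diagnosis to repeat. The fix below respects that.

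**Conclusion.** The gap is real. The entry rules admit EUS diagnoses made with the pathology already known, leave the choice among repeat examinations open, and collect nothing that would allow such cases to be counted, removed or adjusted for. This could bias the only endpoint, most likely upward, and could distort the factor analysis. Over the protocol's 43% to 79% range the bias in the rate is about +0.2 to +11.4 points. That rests on assumed shares of 2% to 20% and assumed known-pathology concordance of 90% to 100%. Confidence is high for the omission and low for the size, which only the records can settle. For the post-removal subset the direction is open as well.

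**What to change.** Put one consistent rule in 5.2 and 5.3:

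*The index EUS is the last EUS of that lesion performed before a diagnostic histological result for it was available. Lesions whose only EUS followed a known diagnostic result are excluded from the primary analysis. A prior non-diagnostic biopsy does not exclude a lesion.*

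Add to 6.4 the date of the index EUS, the date of the first diagnostic histology, and any prior sampling or removal with its result. Report the number of lesions excluded, and repeat the coincidence rate and the logistic model with them included as a sensitivity analysis, stating in advance which EUS is used for those lesions.

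**Cost.** The change needs protocol wording, ethics approval of the amendment (11.3) and a few fields from records already being reviewed. Some lesions leave the primary set. If 5%, 10% or 20% of 269 were excluded, 256, 242 or 215 would remain. Power on the protocol's own model would then be 0.77, 0.74 or 0.68, and the half-width at 43% would go from 5.9 to 6.1, 6.2 or 6.6 points. Keeping 269 eligible cases would need 284, 299 or 337 (269 divided by 0.95, 0.90 or 0.80, rounded up). The reported rate may also be lower.
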